5.7 Re-Entry into Study Treatment

In some circumstances, a participant may temporarily discontinue the study medication and/or not return to the study clinic for follow-up visits. If the participant decides to return for study injections and/or follow-up assessments at a later date, he or she will be allowed and encouraged to do so.

6 PARTICIPANT SAFETY

6.1 Risk, Benefits and Inclusion of Children

The risks of this study are presented in this protocol and in the informed consent form. This study will examine whether ATG-GCSF will preserve beta cell function, but there is no guarantee that this will occur.

There is the prospect of direct benefit to the individual subjects for their participation in the study. These potential benefits include the recognized benefits of being in a clinical study, including close monitoring and additional resources available to maintain tight glycemic control offered to all subjects, regardless of group assignment. Further, the intervention has the prospect of direct benefit to a given subject and is likely to yield general knowledge about T1DM that is of importance for the understanding and amelioration of T1DM in children.

The study procedures, while possibly slightly greater than minimal risk, offer the possibility of benefit in the close monitoring for all children. Assent of children along with consent of the parents will be obtained prior to any study procedures. This research proposal in children is therefore consistent with United States Department of Health and Human Services, Protection of Human Subjects, subpart D, section 46.405 (research involving greater than minimal risk but presenting the prospect of direct benefit to individual subjects) and with Subpart D. 50.52 (Clinical investigations involving greater than minimal risk but presenting the prospect of direct benefit to individual subjects).

6.2 Potential Risks

6.2.1 ATG

ATG has been widely used in transplantation and autoimmune disorders (42). With the low dose, the absence of other immunosuppressive medications, and the lack of severe medical conditions other than T1D we expect minimal side effects. In the ITN study, subjects receive ATG at a total

dose of 6.5 mg/kg, a dose which has been effective and well tolerated in bone marrow and solid organ transplantation, and well below the dose of 20 mg/kg that has been used for some transplantation protocols. For this study, the doses will be administered as 0.5 mg/kg during the first infusion and 2 mg/kg during the second infusion to reduce reactions. ATG will be given slowly by continuous IV infusion over at least a 12 hour period during the first dose and at least an 8 hour period during the second dose. Subjects will receive pre-medication with methylprednisolone, acetaminophen and diphenhydramine to minimize side effects from possible cytokine release syndrome (CRS), and will be closely observed in the hospital during the treatment period. Symptoms of CRS may include fever, chills, rigors, headache, tremor, nausea, vomiting, diarrhea, abdominal pain, muscle and joint pain, and malaise. Anaphylactic reactions have been rarely reported with ATG, but delayed allergic reactions with serum sickness are occasionally observed.

ATG contains a variety of antibodies that may cross-react with cell-surface markers. ATG causes lymphocyte depletion with marked depletion of lymphocytes occurring acutely. The circulating number of T cells increases with cessation of therapy, usually reaching pre-treatment levels by 2 months. Subjects are at low risk for opportunistic infection during this window of recovery and will receive close surveillance for primary viral infections, viral reactivations, and bacterial infections (76, 77).

ATG may also lead to leukopenia and thrombocytopenia. Effects are dose-dependent and are mainly encountered with over dosage. In up to 3% severe thrombocytopenia may occur but this is invariably seen in doses 4-5 times that which we are proposing. Thrombocytopenia in these subjects often occurred in a postoperative transplant setting and with other immunosuppressants. There was no concern for prolonged leukopenia or thrombocytopenia in our pilot ATG-GCSF study.

Transient abnormalities in liver function tests have been described in patients with aplastic anemia treated with ATG preparations. Such adverse events have not been noted in numerous other clinical settings in which ATG has been used, and it is not clear if this is related to the underlying disease or to associated medications used.

Conflicting data exists about the risk of EBV-related lymphoproliferative disease. Furthermore, in renal transplant patients, the overall risk in this transplant population is low (0.25%-0.85%), and patients received several immunosuppressive therapies and were on continuous immunosuppression (42). There were no reported cases of EBV-associated lymphoproliferative disease in over 1,675 treated subjects (including children) treated for aplastic anemia.

6.2.2 GCSF

There are some potential risks associated with GCSF therapy. The side effect profile of GCSF injection will be monitored by close clinical observation of the subjects for 1 hour after the first GCSF injection as well as with daily contact to the subjects during the first 5 days of GCSF/placebo therapy and then weekly until the week 12 visit.

GCSF carries a risk (10-20% of patients) of bone pain and a risk (less than 10%) of headache, fever, pain or redness at the site of injection, and dizziness. According to the company USPI, there is also potential risk of Acute Respiratory Distress Syndrome, serious allergic reactions, and Sickle Cell crisis. There is also a risk that the subjects' WBC could become elevated while taking GCSF. A complete list of the potential risks associated with GCSF is further described in the package insert at http://pi.amgen.com/united_states/neulasta/neulasta_pi_hcp_english.pdf. This will be monitored by the study team at each center and the dose of study drug will be dispensed by the pharmacy as placebo regardless of randomization (to ensure blinding is

protected) if the ANC is $> 35 \times 10^9/L$. There are also now a small number of reports in which recipients of GCSF have developed splenomegaly and/or splenic rupture. This risk will be explicitly discussed in the consent form and subjects will have close physical examination and follow-up to screen for any signs or symptoms. In addition, weekly contact for the month following therapy will be used to document any adverse reactions. The CBC and complete metabolic profile at each blood draw will be carefully reviewed for any clinically relevant abnormalities. There are no other known long-term risks from a 12 week course of GCSF.

6.3 Pregnancy

Female subjects with reproductive potential will be instructed to use effective means of birth control (which includes abstinence) from randomization until 3 months post last infusion of study drug to assure safety. They will also be asked to avoid pregnancy until last scheduled study visit at 24 months post randomization. This is to assure accurate endpoint measurements. They will undergo urine pregnancy testing at the start of every study visit. All pregnancies that are identified during the study must be followed to conclusion and the outcome of each must be reported. The investigator should be informed immediately of any pregnancy occurring in a female participant. Monitoring of the participant should continue until the conclusion of the pregnancy. Subjects that are found to be pregnant while on this study shall have treatment withheld, but will still be followed for safety and other study measures as appropriate. Treatment may only be resumed when subjects are no longer pregnant or nursing.

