3.1.1 Inclusion Criteria

Potential participants must **meet all** of the following inclusion criteria:

1. Must be ≥ 12 years < 46
2. Must have a diagnosis of T1D for less than 100 days at randomization
3. Willing to provide Informed Consent or have a parent or legal guardian provide informed consent if the subject is <18 years of age
4. Positive for at least one islet cell autoantibody; GAD65A, mIAA, if obtained within 10 days of the onset of insulin therapy, IA-2A, ICA, or ZnT8A

5. Must have stimulated C-peptide levels ≥ 0.2 pmol/ml measured during a mixed meal tolerance test (MMTT) conducted at least 21 days from diagnosis of diabetes.
Randomization should occur within one month (37 days) of the MMTT. However, with prior approval by TrialNet, this window may be extended to allow randomization within 8 weeks (56 days).
6. Subjects who are EBV seronegative at screening must be EBV PCR negative within 30 days of randomization and may not have had signs or symptoms of an EBV compatible illness lasting longer than 7 days within 30 days of randomization
7. Be at least 6 weeks from last live immunization
8. Participants are required to receive killed influenza vaccination at least 2 weeks prior to randomization when vaccine for the current or upcoming flu season is available
9. Be willing to forgo vaccines during the treatment period and for 3 months following last dose of study drug
10. Be willing to comply with intensive diabetes management

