3.1.2 Exclusion Criteria

Potential participants must **not** meet any of the following exclusion criteria:

1. Be immunodeficient or have clinically significant chronic lymphopenia: (Leukopenia ($< 3,000$ leukocytes / μ L), neutropenia ($< 1,500$ neutrophils/ μ L), lymphopenia (< 800 lymphocytes/ μ L), or thrombocytopenia ($< 100,000$ platelets/ μ L).
2. Have active signs or symptoms of acute infection at the time of randomization
3. Have evidence of prior or current tuberculosis infection as assessed by PPD, interferon gamma release assay or by history
4. Be currently pregnant or lactating, or anticipate getting pregnant within the two year study period
5. Require use of other immunosuppressive agents including chronic use of systemic steroids
6. Have evidence of current or past HIV, Hepatitis B or Hepatitis C infection
7. Have any complicating medical issues or abnormal clinical laboratory results that may interfere with study conduct, or cause increased risk to include pre-existing cardiac disease, COPD, sickle cell disease, neurological, or blood count abnormalities
8. Have a history of malignancies other than skin
9. Evidence of liver dysfunction with AST or ALT greater than 3 times the upper limits of normal
10. Evidence of renal dysfunction with creatinine greater than 1.5 times the upper limit of normal
11. Vaccination with a live virus within the last 6 weeks

12. Current or ongoing use of non-insulin pharmaceuticals that affect glycemic control within prior 7 days of screening
13. Active participation in another T1D treatment study in the previous 30 days
14. Prior treatment with abatacept or anti-cd3
15. Known allergy to GCSF or ATG
16. Prior treatment with ATG or known allergy to rabbit derived products
17. Any condition that in the investigator's opinion may adversely affect study participation or may compromise the study results

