4.5.2 ATG / Placebo Administration

All participants will be admitted to the hospital for the duration of the infusions and will be discharged no sooner than 12 hours after ATG infusion has been completed. Body weight at baseline (Time 0 – admission for the ATG/placebo infusion) will be used in calculating the doses for all infusions. Allowance in dose administration will be within +/- 5% of calculated dose.

To minimize the risk for thrombophlebitis associated with ATG infusion, 1000 units of heparin and 20 mg of hydrocortisone will be added to the ATG infusion bag for each dose given via peripheral intravenous administration. Since there is only a slight risk for thrombophlebitis for placebo infusion, the heparin and hydrocortisone will not be included in the infusion bag.

The first dose (0.5mg/kg) will be infused over a minimum of 12 hours, and the second dose (2mg/kg) over a minimum of 8 hours. The second dose should be given no less than 12 and no more than 24 hours after the previous dose. A maximum of 60 hours from the start of the first IV infusion will be allowed to complete all IV study drug (see parameters below). If a subject has not completed the two IV study drug infusions at the 60th hour, the infusion will be discontinued and they will not receive additional study drug. Vital signs will be checked every 30 minutes for the first 2 hours of the study drug infusion and thereafter at 60-minute intervals or as indicated for clinical signs or symptoms. Blood for laboratory testing should be drawn at least 8 hours after completion of each infusion in order to obtain reliable and comparable results.

Information about subject's clinical signs and symptoms related to ATG infusion will be captured on infusion CRFs. Those that are Grade 2 or more will be considered AEs and reported as such.

4.6 Premedication:

To reduce the risk of adverse reactions to ATG infusion, methylprednisolone 0.25 mg/kg IV will be given no less than 30 minutes before each infusion of active drug and 0.25 mg/kg IV will be given 12 hours (\pm 15 min) after the start of each infusion of active drug.

Placebo group: A placebo (saline) infusion similar in appearance will be given no less than 30 minutes before and 12 hours (\pm 15 min) after the start of each infusion.

Both groups: Participants in both groups will be pre-medicated with an antihistamine and acetaminophen PO at least 30 minutes before each infusion and every 4–6 hours as needed during the infusion, as follows:

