4.8.1 GCSF / Placebo Administration

GCSF/Placebo treatment will begin 6 hours after completion of the ATG / Placebo. GCSF/Placebo will be given subcutaneously every 2 weeks for a total of 6 doses. Drug vehicle provided by the manufacturer will be used for the placebo injections.

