4.10 Concomitant Medications

The use of concomitant medications will be assessed at each study visit and recorded on an appropriate source document and CRF. Participants are allowed to use preparations of insulin as advised by the investigator or the referring physician.

Participants will be requested not to use any of the following medications during the study.

- Agents that influence insulin sensitivity or secretion (pramlintide, sulfonylureas, metformin, diphenylhydantoin, thiazide, or other potassium-depleting diuretics, beta-adrenergic blockers, niacin).
- Vaccination with live vaccines from 6 weeks before enrollment to 3 months following last dose of study drug is not permitted. Killed vaccines other than influenza are discouraged during this time period.
- Any medication that may result in immunosuppression or immunomodulation.
- Systemic glucocorticoids (unless required during ATG administration or for the treatment of cytokine release syndrome or serum sickness).

If participants receive, or if the investigator believes that participants must receive, any of the above medications, the case must be discussed with the medical monitor and/or treating physician to determine if alternatives are available. The use of these medications must be documented on the source document and CRF.

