5.2 Laboratory Assessments

The following general laboratory assessments will be performed:

- Chemistry (sodium, potassium, chloride, CO₂, glucose, BUN, creatinine)
- Liver function tests (ALT, AST, alkaline phosphatase, total protein, albumin, total and direct bilirubin)
- Hematology (complete blood count with differential and platelets)
- CD4/CD8 ratio
- Serum IgG levels

At screening, these additional laboratory assessments will be performed:

- Interferon-Gamma Release Assay Test (IGRA)
- Diabetes Autoantibodies
- Antibodies to HIV, hepatitis B (antiHBcAb, HBsAg), hepatitis C (HCV), Cytomegalovirus (CMV IgG, IgM), and Epstein-Barr Virus (EBV IgG, IgM, EBNA₁CMV and EBV PCR)

Additional assessments include:

- Pregnancy test before each injection for all sexually mature women

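### Section 6.3 ties the safety-based birth-control period to the last infusion, so read literally it ends about three weeks after the last GCSF/placebo injection

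*Protocol*

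**What the plan says.** Section 6.3 gives one contraception instruction with a safety reason. It runs "from randomization until 3 months post last infusion of study drug to assure safety". The same section then asks women to avoid pregnancy until the 24-month visit, and gives accurate endpoint measurement as the reason. It also says: "Subjects that are found to be pregnant while on this study shall have treatment withheld". Treatment may resume once the woman is neither pregnant nor nursing.

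The two study drugs are given by different routes and on different timetables:

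- **ATG/placebo** is intravenous, in two infusions. Section 4.5.2 states: "A maximum of 60 hours from the start of the first IV infusion will be allowed to complete all IV study drug". Appendix 1 places the infusions on days 1 and 2.
- **GCSF/placebo** is not infused. Section 4.8.1 states: "GCSF/Placebo will be given subcutaneously every 2 weeks for a total of 6 doses". The first dose follows 6 hours after ATG/placebo ends, and Appendix 1 places the last at week 10.

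The two vaccine rules use a different anchor for the same three months. Inclusion criterion 9 (section 3.1.1) reads "Be willing to forgo vaccines during the treatment period and for 3 months following last dose of study drug". Section 4.10 says that live vaccination "from 6 weeks before enrollment to 3 months following last dose of study drug is not permitted".

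Two other provisions bear on the point. Section 5.2 lists a "Pregnancy test before each injection for all sexually mature women", and exclusion criterion 4 (section 3.1.2) bars women who "anticipate getting pregnant within the two year study period".

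**The concern.** The anchor in section 6.3 is reached before any GCSF/placebo has been given. A site that follows the sentence as written would end the safety-based contraception instruction about three weeks after a woman's last study drug, although the protocol elsewhere allows three months from the last dose.

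The anchor also does not move if GCSF/placebo is delayed. Section 5.7 lets a participant who stopped study medication come back for injections later, and section 6.3 lets treatment resume after pregnancy or nursing. Neither sets a latest date. An injection resumed after about day 93 would be given with no safety-based contraception instruction in force.

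**Working it through.** The protocol gives no day on which the birth-control period ends, so there is no figure to reproduce. The dates follow from the schedule.

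**Inputs**

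- Last infusion: day 2 (Appendix 1). At the 60-hour limit with a start on day 1: 1 + 2.5 = day 3.5 (section 4.5.2).
- GCSF/placebo doses: day 2, then weeks 2, 4, 6, 8 and 10, which are days 14, 28, 42, 56 and 70 counted from day 0 (Appendix 1).
- Window for the week-10 visit (Visit 5): ±3 days (section 5.5).
- Assumption: three months is 91 days. Using 90 or 92 moves each end date by one day.

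**Literal end of the instruction** (last infusion + 91)

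- On schedule: 2 + 91 = day 93.
- Infusions run to the limit: 3.5 + 91 = day 94.5.

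**Last GCSF/placebo dose**

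- On schedule: day 70. With the window: 67 to 73.

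**Cover after the last study drug** (literal end − last GCSF/placebo dose)

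- On schedule: 93 − 70 = 23 days.
- Shortest: 93 − 73 = 20 days.
- Longest: 94.5 − 67 = 27.5 days.

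**End under a last-dose anchor** (last GCSF/placebo dose + 91)

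- On schedule: 70 + 91 = day 161. With the window: 158 to 164.
- Difference from the literal end: 161 − 93 = 68 days. Range: 67 − 3.5 = 63.5 to 73 − 2 = 71 days.

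**Sensitivity to the counting origin.** Section 4.8.1 could be read as counting the two-week steps from the first dose on day 2. The last dose is then 2 + 70 = day 72 (69 to 75). Cover becomes 93 − 72 = 21 days, with a range of 93 − 75 = 18 to 94.5 − 69 = 25.5. The last-dose anchor ends at 72 + 91 = day 163, which is 70 days after day 93. About three weeks holds under either count.

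**Does the protocol otherwise support an ATG-only reading?** After the 60-hour limit the only treatment left is GCSF/placebo. The rule that withholds treatment in pregnancy and the test before each injection therefore both apply to GCSF/placebo. Section 6.2.2 also calls GCSF study drug. The protocol thus treats pregnancy as relevant to GCSF/placebo dosing, while the contraception clock ignores those doses.

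**Does scheduled testing cover the difference?** Appendix 1 tests at month 3 (about day 91 ± 3) and next at month 6 (about day 182 ± 7). The interval from day 93 to day 161 lies almost wholly between these two tests.

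**The case against.** The strongest reply is that no harm is shown under either reading of the word.

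- **It may be loose wording.** Section 6.4 mentions infusions and injections together and then speaks only of monitoring around the injection. If *infusion* was meant as *dose*, the intent is sound. This is plausible, but sites work from the written text, and the written text gives the shorter period.
- **ATG may be what was meant.** Section 6.2.1 expects T cells back at pre-treatment levels by about two months, so three months after ATG would be coherent. Section 6.2.2 names no reproductive risk for GCSF. This stands to the extent that 23 days cannot be called inadequate from the protocol. The reading still fits poorly with withholding GCSF/placebo in pregnancy, and the protocol nowhere says that the period concerns ATG alone.
- **The period still covers every dose.** On the planned schedule all six GCSF/placebo doses fall before day 93. That is correct, but it fails for injections resumed later under section 5.7 or 6.3.
- **Other provisions limit the risk.** Women are asked to avoid pregnancy to month 24, exclusion criterion 4 covers two years, and pregnancy is tested at visits. These do reduce the practical risk. But the 24-month request rests on endpoint accuracy, the exclusion concerns intention at entry, and testing detects pregnancy without preventing it.
- **Vaccine and contraception periods need not match.** True. The vaccine rules show only that the protocol has a last-dose wording available and uses it for the same three months.
- **The consent form may already be right.** It is not in the text reviewed, so what participants are told cannot be judged.

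**Conclusion.** The concern holds. The only contraception instruction given for safety is tied to an event that precedes every GCSF/placebo dose. Read literally it ends on about day 93, about 23 days after the last study drug (20 to 28 with visit windows and the 60-hour limit; about 21 if week 10 is counted from day 2). A last-dose anchor would end it on about day 161.

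The figures assume the Appendix 1 schedule and three months of 91 days. The finding is an inconsistent anchor in an operational safety rule. It does not show that three weeks after GCSF is unsafe, since the protocol states no required interval. Confidence is moderate, because *infusion* may be a slip and the consent wording is unseen. The change should be made, but nothing in the statistical design depends on it.

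**What to change.** In section 6.3, replace the reference to the last infusion with *last dose of study drug (ATG/placebo or GCSF/placebo)*. This matches sections 3.1.1 and 4.10, shortens the period by itself if GCSF/placebo stops early, and extends it if injections are resumed late. If only ATG is meant, say so and give the reason. Check that the consent form uses the same anchor.

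The cost is one phrase, a consent check, and about 68 more days of instructed contraception for women who are already asked to avoid pregnancy to month 24.
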